Climate impact label design and fast-food meal selection

NCT06678178

Statistical Analysis Plan

Version Date: 11/05/2024

Statistical Analysis Plan

Research Question and Hypotheses:

The primary objective of this study is to test the relative effects of climate-impact menu label designs on the healthfulness of consumers' fast-food meal choices via a between subjects randomized experiment. We predict that, relative to a control label, a high impact warning label will lead to the healthiest food choices, followed by a three-level traffic-light label, then by a five-level climate impact grade, and finally a numeric carbon footprint label.

We believe the same label performance predictions will apply to our secondary outcomes, including: total greenhouse gas emissions per meal order, total calories per meal order, and selection of a sugar-sweetened beverage.

Key Variables

Primary outcome: Participants will order a hypothetical meal from an online fast-food menu via Qualtrics. Participants will be randomized to one of five label conditions that will appear on the menu: 1) a control label, 2) a high impact warning label; 3) a three-level traffic-light label, 4) a five-level climate impact grade, and 5) a numeric carbon footprint label. The primary outcome will be the healthfulness of each participant's meal selections. This score will be based on the Nutrient Profile Index (NPI) algorithm, which assigns a score from 1-100 scale based on a product's nutritional composition, with items scoring ≥ 64 considered healthy. This measure will be determined by calculating the weighted mean NPI score of all items selected per meal, with each item's NPI score weighted by its proportionate contribution of mass in grams to the total mass of the meal. Beverages will be excluded from the modified score and assessed through secondary outcomes.

Secondary outcomes: Our first secondary outcome is total greenhouse gas emissions of the hypothetical meal ordered measured in kilograms of CO₂ equivalents. This will be calculated for each menu item using nutritional and recipe information from publicly available information combined with data on associated emissions for related food items from the World Resource Institute (WRI) CoolFood Calculator. Total estimated greenhouse gas emissions per meal will be calculated as the sum of estimated emissions for all menu items ordered in a meal.

We will also assess the total calories ordered, and whether or not a sugar-sweetened beverage was selected.

Additionally, we will measure perceived message effectiveness of the various climate-impact labels. Following the meal ordering task, participants will be asked to respond to three statements about perceived message effectiveness of the climate-impact label for which they were randomized to view on the menu. Statements are derived from the UNC-PME scale and will assess

participant levels of discouragement, unpleasantness, and concern regarding high impact menu items when paired the climate-impact label, using a 5-point Likert scale (1= Not at All, 5 = A Great Deal). Participants will also view labels from all five labeling conditions and rank the labels in order of most effective (1) to least effective (5) for communicating the high climate impact of individual menu items.

This is a between-subjects experiment in which participants will be randomized to one of five arms. All participants will view a fast-food online ordering menu, with menus for each study arm differing by the climate-impact labeling scheme applied: (1) a QR code on all items (control); (2) a high climate impact warning label on high impact items; (3) traffic light labels (high-, medium-, and low-impact) on all items by level of impact; (4) climate grade labels (A, B, C, D, F) on all items by level of impact; and (5) numeric carbon footprint labels on all items.

Statistical Analyses

To determine the effects of the four climate-impact labels compared to the control label on our continuous primary outcome of dietary quality, we will regress the outcome onto a categorical indicator representing experimental condition. If the primary outcome is not normally distributed, we will perform appropriate transformations and use robust standard error estimates to preserve valid standard errors and p- values.

We will use a similar approach for secondary outcomes and regress each secondary outcome onto an indicator of experimental arm. For the binary secondary outcome of whether a participant selected a SSB, we will use logistic regression and regress the outcome onto a categorical indicator representing experimental condition. We will compare the odds of selecting an SSB for each experimental condition compared to the control and will use post estimation margins to examine the proportion of participants in each outcome who select an SSB.

We will use predicted margins to examine predicted mean values of each outcome for each experimental condition.

Statistically significant differences will be considered at $p<0.05$ with Bonferroni-Holm correction for multiple comparisons and all tests will be two-tailed.

We will not exclude observations based on values of any of the outcome variables. We will exclude observations of participants who complete the survey implausibly quickly based on the distribution of the time to complete the survey among all participants. We will also exclude participant who fail built-in Qualtrics survey fraud detection measures.

*This analysis plan was pre-registered on AsPredicted on 11/05/2024

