Climate impact label design and fast-food meal selection

NCT06678178

Study Protocol

Version Date: 10/18/2024

BSPH IRB Research Plan for New Data Collection

IRB Version: 01Sep2023

For new data collection, new data collection plus secondary data analysis, biospecimen repositories, and data coordinating center protocols.

DO NOT DELETE ANY QUESTIONS FROM THIS TEMPLATE

PI Name: [name]

Study Title: **Testing climate impact menu labels influence on nutrition quality of fast food selections: a pilot study**

IRB No.: IRB00030419

PI Version No. / Date: V1/October 18, 2024

I. Aims of the Study: *Describe the aims/objectives of the research and/or the project's research questions or hypotheses.*

Our primary objective of this study is to compare the effects of different climate-label menu designs on the healthfulness of hypothetical fast-food meal orders. We hypothesize that: (1) compared to orders from menus with control labels, participants ordering from menus with all other climate-impact labels will select more healthful meal, and (2) the effect of healthfulness of meal orders will differ by climate-impact label condition, with high-impact warning labels performing best, followed by the traffic light labeling scheme, then by the grade labeling scheme, and finally the numeric labels.

As a secondary outcome, we will also seek to compare perceived message effectiveness (PME) of different climate-label menu designs to communicate the environmental impact associated with fast-food menu items. We hypothesize that: (1) participants will perceive climate-impact labels as more effective compared to control labels, and (2) PME will differ by climate-impact label condition, with high-impact warning labels performing best, followed by the traffic light labeling scheme, then by the grade labeling scheme, and finally the numeric labels.

Additional secondary outcomes will include examining total greenhouse gas emissions per meal order, total calories per meal order, and selection of a sugar-sweetened beverage within order.

This is a pilot study to help us determine the label types we will include in our next study using the NORC AmeriSpeak panel (IRB00027451). A separate application exists and will be amended for the next study for IRB approval, prior to its initiation.

II. Background and Rationale: *Explain why this study is being done. Summarize briefly what is already known about the issue and reference previously published research, if relevant.*

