- (4) A numeric labeling scheme that demonstrates the estimated climate-impact associated with the life cycle of each menu item in kilograms of carbon dioxide equivalent (kg CO₂e).

We will also compare effects of these labels against a control condition with a Quick Response (QR) code label on all menu items.

III. Study Design:

- A. *Provide a BRIEF overview of your study design and methods. The study design must relate to your stated aims/objectives. DETAILS WILL BE REQUESTED LATER. If your study also involves analysis of existing data, please complete Section XI, "Secondary Data Analysis of Existing Data" in the last part of this research plan. If your study ONLY involves analysis of existing data, please use the research plan template for secondary data analysis (BSPH IRB Research Plan for Secondary Data Analysis of Existing Data/Specimens).*

We will conduct a randomized controlled experiment in which participants are randomly assigned to view one of five versions of a fast-food menu based on a well-known burger-focused fast-food chain, and instructed to select an entrée they would hypothetically like to order for lunch. Each menu version will differ by labeling condition assigned to main menu items to demonstrate the climate impact associated with each item. Climate-impact label menu designs in the study will include a QR code label (control), a high-impact warning label, traffic-light labeling of high, medium, and low impact, grade labeling (five-tiers; grades A-F) and a numeric label describing the estimated amount of kg CO₂e associated with each menu item. Following the meal ordering task, we will also ask questions about the perceived message effectiveness of the label for which each participant was randomized, their perception of the relative effectiveness of all labels in this experiment, and their personal values, dietary patterns, and other demographic information.

This trial will first be conducted as a pilot study via CloudResearch, an online panel provider, before fielding a larger study with NORC AmeriSpeak, another online panel provider. A separate application (IRB00027451) exists and will be amended for the next study for IRB approval, prior to its initiation.

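### Does the unspecified analysis of the five-label ranking leave the perceived message effectiveness result open?

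*SAP*

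**What the plan says.** Protocol Section I makes perceived message effectiveness (PME) a secondary outcome; the aim is to "compare perceived message effectiveness (PME) of different climate-label menu designs to communicate the environmental impact associated with fast-food menu items". Its ordered hypothesis is that "PME will differ by climate-impact label condition, with high-impact warning labels performing best", with traffic light, grade and numeric labels following.

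The SAP, under Key Variables (Secondary outcomes), opens the relevant paragraph with "Additionally, we will measure perceived message effectiveness of the various climate-impact labels" and then describes two instruments:

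- Three 5-point statements, derived from the UNC-PME scale, about the label the participant was randomised to see. They cover "participant levels of discouragement, unpleasantness, and concern regarding high impact menu items".
- A task in which each participant views all five labels and is asked to "rank the labels in order of most effective (1) to least effective (5) for communicating the high climate impact of individual menu items".

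The SAP's Statistical Analyses section does not mention the ranking. The only rule that could reach it is "We will use a similar approach for secondary outcomes and regress each secondary outcome onto an indicator of experimental arm", followed by predicted means for each condition.

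**The concern.** Two instruments sit under one opening sentence, and they ask different things. The statements ask whether a label discourages or worries the participant; the ranking asks which label communicates best. The two could order the labels differently. The protocol's aim speaks of communicating environmental impact, which is closer to the wording of the ranking than to that of the statements. A reader could therefore fear that the PME result to be reported might be chosen after the data are seen.

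The analysis rule adds to the worry. The ranking is a within-person measure, while the rule compares arms. If the rule were run on the rank given to one particular label, a significant result would mean that seeing a label changes how it is ranked. It could be misread as evidence that one label is preferred to another.

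**Working it through.** **1. Which instrument is PME?** The passages, side by side:

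| Place | What it shows | Points to |
|---|---|---|
| SAP, Key Variables | The PME term and the UNC-PME scale are attached to the three statements; the ranking sentence uses neither | Statements |
| Protocol III.A | "questions about the perceived message effectiveness of the label for which each participant was randomized, their perception of the relative effectiveness of all labels" are listed as separate items | Statements |
| Protocol V.C.1 | Questions on the assigned label come first, then one question on relative effectiveness | Statements |
| Protocol I, hypothesis | The ordering is by label condition, which is a comparison of arms | Statements |
| Protocol I, aim | Effectiveness is worded as communicating impact | Ranking |
| SAP, Key Variables | One opening sentence covers both instruments | Either |
| Protocol V.C.4 | PME is listed; the ranking is not named | Little either way |
| SAP, Research Question and Hypotheses | "our secondary outcomes, including: total greenhouse gas emissions per meal order, total calories per meal order, and selection of a sugar-sweetened beverage" is introduced as a non-exhaustive list | Little either way |

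The statements are the natural test of the PME hypothesis.

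**2. What does the arm rule do with ranks?** Five ranks sum to 1+2+3+4+5 = 15, so each participant's mean rank is 15/5 = 3.0 in every arm and carries no information. Two other outcomes are possible:

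- *The rank of one fixed label, regressed on arm.* This compares differently exposed groups on the same label, so it tests exposure.
- *Each participant's rank of the assigned label, regressed on arm.* This compares labels between participants, because each arm contributes ranks of its own label.

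A simulation shows the difference. The 1,250 per arm is from Protocol III.B. The preferences are assumed: Plackett-Luce utilities of 0, 1.0, 0.8, 0.5 and 0.2 for QR, warning, traffic light, grade and numeric, times a multiplier. The test is a one-way F test at 0.05, with 300 to 1,000 runs per setting.

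| Assumed truth | Fixed-label rank on arm | Own-label rank on arm | Friedman, within person |
|---|---|---|---|
| Equal labels, no exposure effect | about 5% | about 5% | about 5% |
| Multiplier 1, no exposure effect | about 5% | 100% | 100% |
| Multiplier 2 (mean ranks 1.96 to 4.04), no exposure effect | about 5% | 100% | 100% |
| Equal labels, shown label has mean rank 2.90 | about 60% per label | about 5% | about 5% |

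In the last row the other arms give that label a mean rank of (15 − 2.90)/4 = 3.025. Own-label rank then has the same distribution in every arm, so its true rejection rate is the nominal 5%.

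The fixed-label version answers a different question, but the arm rule is not incapable of comparing labels. The SAP simply does not define which variable it would use.

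**3. How well would a plain summary serve?** With N = 6,250 and random ranks, the variance of one rank is (5² − 1)/12 = 2.

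- Mean rank: 1.96 × √(2/6,250) = 0.035.
- Share ranking a label first, at 20%: 1.96 × √(0.2 × 0.8/6,250) = 0.0099, about 1.0 percentage point.

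Per-label summaries would be precise without any model.

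**The case for a change.** The strongest case for a change is that the plan was pre-registered to settle such choices in advance, and two or three sentences would settle this one at no cost to participants. If the heading makes the ranking a secondary outcome, the arm rule applies and, on a fixed label's rank, misses the point. If the ranking is descriptive, nothing says so. With no true label differences, ten pairs per measure and Holm correction within each, the chance of at least one significant pair is about 4% on one measure and about 8% if either of two independent measures may be reported.

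Part of this stands: the ranking's status and summary are not written down, and the aim's wording leaves some ambiguity. The rest is weaker. The 8% needs a formal test on ranks that the SAP does not name, independence between the two instruments, and a free choice between them that most of the passages do not support. Testing the three statements one by one would raise it to between 11% and 15%, but that comes from how the statements are combined and has nothing to do with the ranking. The 60% needs an assumed exposure shift and an analysis that no passage commits to.

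**Conclusion.** This is missing detail that analysts would fill sensibly, and no change to the plan follows. The PME hypothesis is tested by the three statements compared between arms, and that result is sound whatever is done with the ranking. A supplementary ranking would ordinarily be reported label by label, to about ±0.035 on a mean rank. The primary outcome and the other secondary outcomes are unaffected, and no passage makes the ranking the basis for choosing labels for the next study.

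The conclusion rests on reading the statements as the PME measure, which most of the relevant passages support, and on the absence of any stated hypothesis about ranks. The rejection rates depend on assumed preferences and serve only to show what each analysis responds to. If a test on ranks were reported as confirming the PME hypothesis, the issue would have to be looked at again; nothing in the documents proposes that.

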B. Provide a sample size and a justification as to how you arrived at that number. If you use screening procedures to arrive at a final sample, distinguish the screening sample size from the enrolled sample size; a table may be helpful. For electronic survey studies involving online recruitment and survey completion: consider how you will set controls on how many people will join your study.

The CloudResearch initial sample will be 6,250 people, evenly divided with approximately 1,250 people in the control arm and each of the four experimental arms, respectively. This sample size will give us >80% power to detect a small effect size (d=0.12) with a conservative Bonferroni adjusted alpha of 0.0125, which was determined based on our prior research would be sufficient to see differences between all label arms. The CloudResearch sample will be broadly representative of the U.S general population, but carry the possibility of a 25% skew tolerance across demographic lines. We will recruit individuals until the target sample size has been reached by working with the managed research partner with CloudResearch.

C. Does your study meet the NIH definition of “clinical trial”: “A research study in which one or more human subjects are prospectively assigned to one or more interventions (which may include placebo or other control) to evaluate the effects of those interventions on health-related biomedical or behavioral outcomes”? If yes, the study must be listed on clinicaltrials.gov, study personnel must complete GCP training, and federally funded studies must post consent forms on approved sites, like clinicaltrials.gov.

Yes.

IV. Participants:

Describe the study participants and the population from which they will be drawn. Specify the inclusion and exclusion criteria. If you plan to include children, note their ages and whether you will include children in foster care or who are wards of the State. Note if the participants are particularly vulnerable in terms of cognitive limitations, education, legal migration status, incarceration, poverty, or some combination of factors.

A. Inclusion Criteria:

- 18 years of age or older
- Residing in the United States
- Member of the CloudResearch panel

B. Exclusion Criteria:

- Under 18 years of age
- Not residing in the United States
- Completed the survey implausibly quickly based on the distribution of the time to complete the survey among all participants

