Participants will complete an approximately 3-minute anonymous online survey. The survey will begin with a written consent statement to which participants can select a multiple choice option to agree and proceed with the survey. Alternatively, participants can opt to decline to provide consent and end the survey. Participants who consent will be automatically randomized into one of five trial arms and presented with a survey, which mimicks a fast-food menu based on a well-known burger-focused fast-food chain, and instructed to select an entrée they would hypothetically like to order for lunch. Participants in each trial arm will be exposed to a menu version that differs by labeling condition assigned to main menu items (e.g., burgers, wraps, salads, etc.) that describes the climate impact associated with each item. Climate-impact label menu designs in the study will include a QR code label (control), a high-impact warning label, traffic-light labeling of high, medium, and low impact, grade labeling (five-tiers; grades A-F) and a numeric label describing the estimated amount of kg CO₂e associated with each menu item. Following the meal ordering task, participants will be presented with several questions about the label for which each participant was randomized to view, followed by a question about relative effectiveness of all labels in the experient. Finally, participants will answer several demographic questions, after which the survey will conclude. CloudResearch will provide information about participants' age, sex, and race and ethnicity, so these questions will not need to be asked.

2. Describe the number and type of study visits and/or contacts between the study team and the participant, how long they will last, and where/how they will take place.

Participants will take the survey, online on a computer or cell phone, at a place of their choosing. They will only take the survey once. The survey is expected to last approximately 3 minutes or less. There is no direct contact between the study team and the participant.

3. Describe the expected duration of the study from the perspective of the individual participant and duration overall.

The survey is expected to last approximately 3 minutes or less.

4. Provide a brief data analysis plan and a description of variables to be derived.

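### The SAP models contain only the arm indicator; prespecified adjustment for panel-supplied age, sex and race/ethnicity would add a small amount of precision at little cost

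*SAP*

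**What the plan says.** The SAP (Statistical Analyses) describes the primary model for meal healthfulness, the Nutrient Profile Index (NPI) score, in one clause: "we will regress the outcome onto a categorical indicator representing experimental condition". For the secondary outcomes it will "regress each secondary outcome onto an indicator of experimental arm", with logistic regression for SSB selection and predicted margins for each outcome. Neither the SAP nor the protocol's analysis paragraph (V.C.4) names a covariate or an adjusted sensitivity analysis. Randomisation is described only as a function of the survey software (protocol V.C.5.A), with no stratification, so the model leaves out no design factor.

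On available data, protocol V.C.1 says: "CloudResearch will provide information about participants' age, sex, and race and ethnicity, so these questions will not need to be asked". It does not say whether the panel's information is complete. Personal values and dietary patterns are asked in the survey after the ordering task (protocol III.A).

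On size, protocol III.B says: "The CloudResearch initial sample will be 6,250 people, evenly divided with approximately 1,250 people in the control arm and each of the four experimental arms". It claims ">80% power to detect a small effect size (d=0.12) with a conservative Bonferroni adjusted alpha of 0.0125" and adds that this "would be sufficient to see differences between all label arms". The SAP tests at 0.05 "with Bonferroni-Holm correction for multiple comparisons and all tests will be two-tailed".

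**The concern.** Baseline variables that predict an outcome explain part of its residual variance. Including them in a linear model narrows the intervals around the arm differences without enrolling anyone. Here three such variables are expected from outside the survey, so conditioning on them cannot introduce post-exposure bias, yet the plan does not use them.

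Precision matters in this trial. The target difference is small (d = 0.12), the pilot is meant to choose the labels for the next study, and the protocol plans six label-versus-label contrasts besides the four against control. Naming the covariates in advance would also prevent a later choice between adjusted and unadjusted results.

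**Working it through.** **Inputs.** n = 1,250 per arm, d = 0.12 and alpha = 0.05/4 = 0.0125 (protocol III.B); two-sided tests (SAP, Statistical Analyses). Excluded participants are replaced (protocol IX.A), so no loss is applied. The R² of age, sex and race/ethnicity is in neither document and is assumed over a range.

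**The protocol's own figure.** On the standardised scale (SD = 1):

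- SE of one contrast = √(2/1250) = 0.040
- Noncentrality = 0.12/0.040 = 3.0
- Critical value for two-sided 0.0125 = 2.498
- Power = Φ(3.0 − 2.498) = 69.2% (a noncentral-t calculation also gives 69.2%)

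The stated figure of more than 80% therefore does not reproduce. Reaching 80% would take 1,549 per arm; with 1,250 per arm, the difference detectable at 80% power is d = 0.134. A one-sided reading gives 77.6%, which is still short and contradicts the SAP's two-tailed rule. If all ten pairs share the correction (alpha 0.005), power is 57.7%.

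**Effect of adjustment in a linear model.** The residual SD becomes √(1 − R²), so SE = 0.040 × √(1 − R²) and the noncentrality is 3.0/√(1 − R²). The equivalent number of extra participants per arm is 1250 × [1/(1 − R²) − 1].

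| Assumed R² | SE reduction | Power | Equivalent extra participants per arm |
|---|---|---|---|
| 0 | 0% | 69.2% | 0 |
| 0.01 | 0.5% | 69.8% | 13 |
| 0.02 | 1.0% | 70.3% | 26 |
| 0.05 | 2.5% | 71.9% | 66 |
| 0.10 | 5.1% | 74.7% | 139 |
| 0.20 | 10.6% | 80.4% | 312 |

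Over R² of 0.01 to 0.05 the gain is 0.5 to 2.7 power points. Setting the required n equal to 1,250 gives the R² that would restore 80%: 1 − 1250/[2 × ((2.498 + 0.842)/0.12)²] = 1 − 1250/1549 ≈ 0.193.

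**Effect in the logistic model.** The table does not carry over to SSB selection. Adding covariates to a logistic model changes the arm odds ratio from marginal to conditional and does not shrink the standard error of its logarithm. A precision gain is available only for a standardised contrast, that is, adjusted proportions and their differences averaged over the sample. The SAP's planned margins step can produce these.

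**The case against.** The strongest reply is that nothing here is wrong. Regressing the outcome on randomised arm is unbiased and gives valid tests, and no passage promises adjustment. With about 1,250 per arm, chance demographic imbalance should be small and is already reflected in the unadjusted standard error. All of this stands. A reader might infer that the arm-only analysis is biased or defective; the documents do not support that.

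The benefit is also assumed. Nothing in the documents shows that age, sex or race/ethnicity predicts a mass-weighted NPI score for a hypothetical order, or predicts the other outcomes. That stands too. It is why the gain is given as a range and why the rows at 0.10 and 0.20 show sensitivity only.

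A reader might infer that adjustment would bring power up to the stated level. At the protocol's alpha that needs an R² of about 0.19, for which there is no evidence. The 69.2% is a floor for a family of four tests, because the SAP uses Holm and not single-step Bonferroni. Simulating Holm over the four label-versus-control tests gives about 69% power per contrast if one label works and 78% if all four do. Even with all four labels at d = 0.12, the unadjusted plan falls short of 80%. An R² of 5% would bring that one case to about 80%, but equal effects for all labels are not what the trial hypothesises.

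Two further inferences go too far. One is that the panel data are complete for every participant: "age, sex, and race and ethnicity, so these questions will not need to be asked" says what will be provided, not how fully. The other is that the change is free. The plan was pre-registered on 11/05/2024, so the primary model would change on the record, and two estimates of the primary outcome could differ. These points limit the recommendation but do not remove the case for adjusting the continuous outcomes.

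**Conclusion.** The point holds as a modest efficiency improvement. The models are arm-only, and baseline variables that assignment cannot affect are expected from the panel. Using them in the linear models should narrow the contrasts slightly: about 0.5% to 2.5% off the standard error and 0.5 to 2.7 power points, if R² lies between 1% and 5%. That range is an assumption, and R² may differ between outcomes.

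The gain applies to the continuous outcomes: NPI, greenhouse gas emissions (GHGE), calories and perceived message effectiveness (PME). It does not apply to the SSB odds ratio. The overstated power in protocol III.B is a separate and larger problem that this change does not solve.

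**What to change.** Before outcomes are examined by arm, amend the SAP as follows.

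- **Continuous outcomes (NPI, GHGE, calories, PME):** add panel-supplied age, sex and race/ethnicity as covariates in the linear models, with robust standard errors. State the form of age, the race/ethnicity categories, and a missing category for blanks.
- **Sensitivity analysis:** keep the arm-only model, and say in advance which model is primary.
- **SSB selection:** either keep the planned unadjusted odds ratio, or report covariate-standardised marginal proportions and differences from the planned margins step. If an adjusted odds ratio is shown, note that it is conditional and that its standard error does not shrink.
- **Variables to leave out:** do not adjust for personal values or dietary patterns, which are asked after the ordering task and could be influenced by the label.
- **Related wording:** protocol V.C.4 names logistic regression for the primary outcome while the SAP treats that outcome as continuous. The two should be reconciled so that the covariates enter one agreed model.

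The cost is a short SAP paragraph, a documented change to the pre-registered model and slightly more analysis work, in return for a small gain. No new data or participants are needed. The power statement in protocol III.B should be corrected separately.
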